6.4.2 Sample Size Considerations

A total sample size of $N=50$ would allow for an estimate of an Odds Ratio of 2.0-3.0 for the rate of persons successfully in community buprenorphine treatment at 4 weeks post-release (71% vs. 30% success favoring XRB; two-sided alpha of 0.05; 80+% power). The proposed sample size will not provide a definitive test of intervention efficacy, but is sized for feasibility testing.

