5.3.1 Number of Participants

N=50. A total sample size of N=50 would allow for an estimate of an Odds Ratio of 2.0-3.0 for the rate of persons successfully in community buprenorphine treatment at 4 weeks post-release (71% vs. 30% success favoring XRB; two-sided alpha of 0.05; 80+% power).

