6.4.1 Statistical Design

This pilot study is exploratory, and Aim 1 is a qualitative estimation of the feasibility and acceptability of this new form of buprenorphine in a large urban jail setting. The study will be moderately well-powered using a superiority contrast ($A \gg B$) of XRB vs. SLB surrounding Aim 2, retention in treatment post-release. Current rates of successful retention in community buprenorphine treatment immediately at one month post-release are 30% or lower (6). This current administrative data reflects closely results seen in an original BUP vs. methadone NYC jail RCT conducted in 2006-2008 (7). If XRB retention at one month post-release (Week 4) is 70% or greater, the study would be powered to detect a significant difference between arms. Analysis of treatment retention among XRB vs. SLB will consist of simple 2x2 tables for counts and proportions of weeks retained in treatment by arm. We are unlikely to extensively model and control for confounders or interaction terms.

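### The sample-size statement pairs an odds ratio of 2.0-3.0 with 80+% power, but its own 71% vs 30% is an odds ratio of 5.7; at 2.0-3.0 power is only about 15-50%

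*Combined protocol and SAP*

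**What the plan says.** Section 6.4.2 (Sample Size Considerations) says that 50 participants "would allow for an estimate of an Odds Ratio of 2.0-3.0 for the rate of persons successfully in community buprenorphine treatment" at 4 weeks post-release. The parenthesis closing that sentence gives the assumptions: "71% vs. 30% success favoring XRB; two-sided alpha of 0.05; 80+% power". Section 5.3.1 (Number of Participants) makes the same statement: "A total sample size of N=50 would allow for an estimate of an Odds Ratio of 2.0-3.0", with the same rates, alpha and power.

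Section 6.4.1 (Statistical Design) describes the comparison through rates alone. For the control side it says: "Current rates of successful retention in community buprenorphine treatment immediately at one month post-release are 30% or lower". It then says that if week-4 XRB retention "is 70% or greater, the study would be powered to detect a significant difference between arms". It plans 2x2 tables but names no test. Section 6.4.2 goes on to say that the trial is sized for feasibility and is not a definitive efficacy test. Nothing in the document reconciles the odds ratio of 2.0-3.0 with the rates beside it.

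**The concern.** An odds ratio follows directly from two proportions, so a sentence that gives both can be checked by hand, and this one fails. Its odds ratio describes a moderate effect and its rates describe a very large one. The power figure can belong to only one of them.

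This is the only comparison in the trial for which power is claimed. A reader who takes the odds ratio at face value would think that 50 participants are enough to pick up a doubling or tripling of the odds of being in treatment. A non-significant result could then be read as evidence against an effect of that size, when the trial would probably have missed it. A later trial could also carry the wrong effect size into its own planning.

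**Working it through.** **Inputs.** Total 50 (5.3.1, 6.4.2); 1:1 allocation (6.1.3), so n = 25 per arm; p1 = 0.71 for XRB, p2 = 0.30 for SLB, two-sided alpha 0.05 and 80+% power (6.4.2). No dropout is applied because the sample-size section states none. As no test is named, three are shown: the pooled-variance normal approximation, and Fisher's exact and Pearson chi-square tests by full enumeration of two binomials with n = 25.

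**1. Reproduce the stated power at 71% vs 30%.** With p̄ = 0.505:

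- SE under the null = √(2 × 0.505 × 0.495/25) = 0.1414
- SE under the alternative = √((0.71 × 0.29 + 0.30 × 0.70)/25) = 0.1290
- z = (0.41 − 1.96 × 0.1414)/0.1290 = 1.03, so power = 84.8%

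Fisher gives 80.5% and Pearson 87.6%. The 80+% reproduces.

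**2. Effect measures from the plan's rates.**

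- 71% vs 30%: OR = (0.71/0.29)/(0.30/0.70) = 5.71; RR = 0.71/0.30 = 2.37; difference = 41 points
- 70% vs 30% (the threshold in 6.4.1): OR = (0.70/0.30)/(0.30/0.70) = 5.44

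Neither odds ratio is near 2.0-3.0. The risk ratio falls inside that range.

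**3. XRB rate implied by the stated odds ratio.** With SLB odds of 0.30/0.70, p1 = OR × (0.30/0.70)/(1 + OR × (0.30/0.70)). This gives 46.2% at OR 2.0, 51.7% at OR 2.5 and 56.3% at OR 3.0, all well short of 71%.

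**4. Power with 25 per arm, SLB rate 30%.**

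| Odds ratio | XRB rate | Normal | Fisher | Pearson | n per arm for 80% (normal) |
|---|---|---|---|---|---|
| 2.0 | 46.2% | 21% | 15% | 24% | 141 |
| 2.5 | 51.7% | 34% | 27% | 38% | 80 |
| 3.0 | 56.3% | 46% | 40% | 51% | 55 |
| 5.71 | 71% | 85% | 80.5% | 88% | 23 |

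The n per arm is [1.96 √(2p̄(1−p̄)) + 0.842 √(p1(1−p1) + p2(1−p2))]² / (p1−p2)². At OR 3.0 it is 54.7 and at OR 2.0 it is 140.7, both rounded up. By the normal approximation, the smallest odds ratio with 80% power at N=50 is about 5.1 (68.7% vs 30%).

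**5. Does another reading rescue the sentence?**

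- *Another control rate.* Normal-approximation power across OR 2.0-3.0 is 18-41% at a 20% control rate, 22-47% at 40% and 22-44% at 50%.
- *One-sided testing* at a 30% control rate: 32-59%.
- *Estimation only.* For an observed OR of 3.0 with 30% under SLB, the SE of the log odds ratio is √(1/14.06 + 1/10.94 + 1/7.5 + 1/17.5) = 0.594. The 95% interval is exp(1.099 ± 1.96 × 0.594), or 0.94 to 9.6.
- *Risk ratio of 2.0-3.0.* The low end, 60% vs 30%, has 57% power by normal approximation and 51% by Fisher.

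**The case against.** The strongest reply is that the design itself is sound. N=50, alpha, the two rates and 80+% power agree with one another, and only the label on the effect measure is wrong. The true assumption stands in the same sentence, and 6.4.1 states the powering condition in rates without any odds ratio. Retention is a secondary objective of a self-described exploratory pilot whose primary outcome is feasibility, and 6.4.2 disclaims a definitive efficacy test. The text also speaks of estimating, not detecting, an odds ratio.

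Much of this stands. The sample size is not in question, and the pilot setting and the disclaimer limit the harm. It is also fair that the trial reaches 80% power slightly below 5.7, at about 5.1 by normal approximation, and that 70% in one section and 71% in another do not contradict each other, since 71% meets a threshold of 70% or more.

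The contradiction remains. The sentence ties the odds ratio to an alpha and a power, so it reads as a power statement. Taken purely as estimation it does no better, because the interval around 3.0 runs from below 1 to nearly 10. Section 6.4.1 presents retention as a superiority contrast with moderately good power. The risk-ratio explanation is plausible but is an inference, and it would confirm that the wording is wrong.

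**Conclusion.** The concern holds. The odds ratio in 5.3.1 and 6.4.2 is inconsistent with the rates given beside it: 71% vs 30% is an odds ratio of 5.7, roughly two to three times the range stated. The 80+% power belongs to the rates. At an odds ratio of 2.0-3.0 power is 21-46% (normal), 15-40% (Fisher) or 24-51% (Pearson), so the trial would miss significance in about half to 85% of repetitions, depending on the test and the effect.

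These figures assume 25 analysed per arm, a 30% SLB rate, a two-sided 0.05 test and no dropout. The conclusion does not depend on which standard 2x2 test is chosen, nor on the SLB rate over the 20-50% range examined. What must be corrected is the stated effect size; the number of participants can stay as it is.

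**What to change.** In both 5.3.1 and 6.4.2, replace the odds ratio of 2.0-3.0 with an odds ratio of about 5.7 (risk ratio about 2.4, risk difference 41 percentage points) for 71% vs 30%. Add one sentence saying that power at an odds ratio of 2.0-3.0 is about 15-50% depending on the test, and name the test to which each figure applies.

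As an editorial matter, use one XRB rate in 6.4.1 and 6.4.2. The choice has a small effect: at 70% vs 30% power is 83% by normal approximation but 78% by Fisher, just under the stated 80%.

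Optionally, show power for an SLB rate above 30%, since 3.3.1 says the SLB arm receives compensation and encouragement beyond usual care. The document gives no figure for this. Taking 40% as an assumed illustration, 70% vs 40% has 57% power by normal approximation and 51% by Fisher.

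The cost is two corrected sentences and one added. No participants, visits or design features change. The stated detectable effect becomes less favourable, but it then matches the calculation.

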6.4.3 Handling of Missing Data

Follow-up among individual participants at Bellevue Hospital is encouraged with XOR's monetary incentives and tracking protocols. Participants in either arm choosing buprenorphine f/u at Bellevue will be particularly likely to complete follow-up. Administrative and program data covering community pharmacy fills of buprenorphine products and community provider reporting will be used to supplement treatment retention outcomes (Aim 2). Missing opioid urine toxicology data is considered MissingAsPositive.

7 - Trial Administration

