Sublingual Buprenorphine (SUBOXONE, Zubsolv, or generic tablets): SLB is administered sublingually or buccally as a single daily dose. Medication should be prescribed in consideration of the frequency of visits. Provision of multiple refills is not advised in early treatment or without appropriate follow-up visits. After treatment induction and stabilization, the maintenance dose of SLB is generally in the range of 4mg/1mg buprenorphine/naloxone to 24mg/6mg buprenorphine/naloxone per day depending on the individual patient and clinical response, as determined by the clinician. Daily doses will vary by individual. The recommended target dose of SLB during maintenance is 16mg/4mg buprenorphine/naloxone. SLB will be prescribed and provided via observed dosing in-jail (controlled substances are not self-administered in-jail) per usual care protocols. Post-release, all participants may elect to continue SLB maintenance with the Bellevue Primary Care Addiction Medicine clinic, or may pursue SLB maintenance from non-NYU/Bellevue community providers. SLB is available free of charge to uninsured patients at Bellevue Hospital Center, or participants may fill SLB prescriptions at community pharmacies. SLB medication will not be provided by the study itself. Self-report, BHC EMR records, and NYS Prescription Monitoring Plan audits will document SLB post-release community treatment retention, daily dose, and refill frequencies.

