6.3.1 Study Schedule

The total number of expected visits per participant is 6 visits. All participants will be given the option to participate in a 24 week therapeutic extension study of XRB treatment following completion of Visit 5 Week 8. If a participant elects to continue and/or initiate XRB treatment, there will be 12 total visits per participant. The average time needed to complete each visit will be approximately one hour. The initial week 0 screening and randomization visit will be conducted in a Rikers Island jail facility in the Opioid Treatment Program. Once consented, enrolled, and randomized, buprenorphine extended-release (XRB) or sublingual buprenorphine (SLB) daily maintenance will be provided per usual Opioid Treatment Program protocols in-jail and prior to release. The timing between randomization and release will vary. Typical misdemeanor sentences in NYC are 30-60 days, and participants may randomize at any time during this incarceration period, begin XRB vs. SLB treatment, and then leave jail after weeks-to-months. This variable, naturalistic, in-custody study period remains Study Week 0. Study Week 1 commences with the day of release from jail. Post-release, all study visits will be conducted at Bellevue Hospital Center's (BHC) Addiction Medicine clinic. Medical and research visits will be conducted weekly and then bi-weekly for both medication arms post-release (week 1 post-release, week 2, week 4, week 6, week 8). The medication schedule for both arms is as follows:

Buprenorphine Extended-Release: Participants randomized to this arm will receive at least two doses of XRB. The first will be administered at study week 0 in-jail, at least one week prior to release. Participants incarcerated for greater than 4 weeks following randomization will receive 2+ XRB doses prior to release. Post-release, XRB injections will be administered at study week 1-16 in the BHC Addiction Medicine clinic depending on the timing of the previous pre-release/community injections.

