Sublingual Buprenorphine: Participants randomized to this arm will be provided SLB daily maintenance per usual Opioid Treatment Programs protocols in-jail. Post-release, SLB arm participants will receive follow-up care at Bellevue Hospital's Addiction Medicine or at non-BHC/NYU community providers, per their preference. We expect and will encourage most participants to follow-up at Bellevue, though this is not mandated. Typically an initial week's supply of SLB is prescribed within one week of release. At visit 2, week 2, SLB participants typically refill a two week's supply of daily maintenance SLB. SLB participants will continue to receive 2-4 week refill prescriptions for SLB from visit 2, week 2 through visit 6, week 8. Regardless of SLB prescribing patterns, they are encouraged to attend study follow-up visits at BHC per the same study schedule (Weeks 1,2,4,6,8). After the completion of Visit 5 Week 8, SLB participants will be offered XRB treatment in the 24 week therapeutic extension. If interested, participants would receive one or more XRB injections during the

period of Weeks 8, 12, 16, 20, 24, and 28 followed by a final safety documentation visit at Week 32.

For both treatment arms, urine toxicology tests will be conducted at all follow-up visits at the BHC Addiction Medicine Clinic in order to detect any illicit substance use as well as buprenorphine adherence.

STUDY SCHEDULE												
Test/Procedures	Screening/ Randomization	Treatment Period & Follow-Up					XR-B 20 Week Treatment & Follow-Up					
Study Visit Number	0	1	2	3	4	5	6	7	8	9	10	11
Week	0	1	2	4	6	8	12	16	20	24	28	32
Informed Consent ¹	X											
HIPAA ²	X											
Locator Form	X											
Medical History	X											
Psychological History	X											
Physician Progress Note	X	X	X	X	X	X	X	X	X	X	X	X
Confirm Eligibility	X											
Randomization	X											
Adverse Event Forms (AE, SAE, BUP specific AE)		X	X	X	X	X	X	X	X	X	X	X
Clinical Assessment of Intervention ³						X						X
Urine Toxicology		X	X	X	X	X	X	X	X	X	X	X
Pregnancy Test				X		X		X			X	
Demographics	X											
MOUD History/Preference	X											
ASI-Modified Lifetime/CJS-Baseline	X											
Timeline Followback	X	X	X	X	X	X	X	X	X	X	X	X
Inmate Lookup Form⁴		X	X	X	X	X						
New Arrests and Days Incarcerated Form⁴		X	X	X	X	X						
Overdose Form		X	X	X	X	X	X	X	X	X	X	X
XR-B Administration Form	X			X			X	X	X	X	X	

NYS Prescription Monitoring Data (SLB- Only)		X	X	X	X	X						

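### Section 6.4.3 counts every missing opioid urine as positive and plans no sensitivity analysis, so an attendance gap between arms could pass for a difference in opioid use, in a direction the documents do not fix

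*Combined protocol and SAP*

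**What the plan says.** The missing-data rule in section 6.4.3 is "Missing opioid urine toxicology data is considered MissingAsPositive". It has no exception. Nothing elsewhere in the document gives an observed-only analysis, another imputation or a count of missing urines by arm. The 2x2 tables in section 6.4.1 are described for retention only, and the pharmacy and provider data in section 6.4.3 supplement retention only.

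On where urine is obtained, section 6.3.1 says "urine toxicology tests will be conducted at all follow-up visits at the BHC Addiction Medicine Clinic". Section 5.1.2 places all follow-up at Bellevue.

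On where treatment is obtained, the arms differ. Post-release, "XRB injections will be administered at study week 1-16 in the BHC Addiction Medicine clinic" (section 6.3.1). By contrast, "SLB arm participants will receive follow-up care at Bellevue Hospital's Addiction Medicine or at non-BHC/NYU community providers, per their preference" (same section). Section 6.4.3 itself links site of care to attendance: "Participants in either arm choosing buprenorphine f/u at Bellevue will be particularly likely to complete follow-up".

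Other text points towards balance or the opposite way. SLB participants have the same visit schedule: "Regardless of SLB prescribing patterns, they are encouraged to attend study follow-up visits at BHC per the same study schedule". Section 6.3.1 also expects most participants to follow up at Bellevue. Section 3.3.1 gives the SLB arm the same compensation and encouragement. Section 5.1.2 describes community tracking, including home visits.

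The outcome affected is illicit opioid use after release (the Secondary Aim 2 hypothesis in section 4.1 and the clinical effectiveness objective in section 4.3).

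**The concern.** A missed Bellevue visit becomes a recorded positive urine. If one arm misses more visits, it collects more recorded positives whether or not its members used opioids. Missing-as-positive is often thought of as conservative. That holds for the level of use within one arm, but not for a difference between arms when attendance may differ by arm.

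At stake is the interpretation of the urine part of the illicit-opioid-use comparison. If only missing-as-positive results are prespecified, nothing in the plan shows how much of a difference, or of an absence of one, comes from attendance. The trial is also unblinded (section 6.1.4), so an alternative handling chosen after results are seen would carry less weight than one written down now.

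**Working it through.** **Plan's own figures.** The plan states no attendance rate, urine positivity or power for the urine outcome. Its only computable figure is for retention: 80+% power for 71% vs 30% at N=50. That reproduces (84.8% by normal approximation, 80.5% by exact Fisher test, 25 per arm), but it says nothing about urine.

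**Inputs from the documents.** N=50 (section 5.3.1) and 1:1 allocation (section 6.1.3) give 25 per arm. Urine is scheduled at weeks 1, 2, 4, 6 and 8 (section 6.3.1), so 5 x 25 = 125 urines per arm through week 8. A 10-point attendance gap is 0.10 x 125 = 12.5 urines.

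**Assumed inputs.** Attendance a and the true positivity m of missed urines.

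**Formula.** The rule inflates an arm's recorded positivity by (1 - a)(1 - m). The false difference, SLB minus XRB, is

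(1 - a_SLB)(1 - m_SLB) - (1 - a_XRB)(1 - m_XRB).

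With equal m this is (a_XRB - a_SLB)(1 - m).

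| m, equal in both arms | Gap of 10 points | Gap of 20 points |
|---|---|---|
| 20% | 8 | 16 |
| 40% | 6 | 12 |
| 60% | 4 | 8 |
| 80% | 2 | 4 |
| 100% | 0 | 0 |

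Reversing the gap reverses the sign. Equal attendance protects only if m is also equal. At 70% attendance in both arms, m of 40% in XRB and 60% in SLB gives 0.3 x 0.4 - 0.3 x 0.6 = -0.06, or 6 points against XRB.

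**Size against sampling error.** Take 40% positivity throughout, with attendance of 80% in XRB and 60% in SLB. Recorded positivity is 1 - 0.8 x 0.6 = 52% and 1 - 0.6 x 0.6 = 64%. At one visit the 95% margin for that difference is 1.96 x sqrt(0.52 x 0.48/25 + 0.64 x 0.36/25) = 1.96 x 0.139 = about 27 points. The 12-point bias is under half of this.

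**Effect on testing.** No urine test is named. Exact enumeration at one visit with 25 per arm, two-sided 0.05, 40% positivity in attenders and missers alike, and no true difference:

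| Attendance, XRB vs SLB | Fisher | Uncorrected chi-square |
|---|---|---|
| 70% vs 70% | 3.1% | 6.2% |
| 80% vs 70% | 4.8% | 8.8% |
| 80% vs 60% | 9.7% | 16.0% |

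The chi-square test is above 5% even with no gap, so at 80% vs 70% only 8.8 - 6.2 = 2.6 points come from attendance.

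**What a sensitivity analysis would show.** Suppose 20/25 XRB and 15/25 SLB participants attend, with 8/20 and 6/15 positive (40% each). Missing-as-positive gives 13/25 = 52% and 16/25 = 64%, a 12-point difference favouring XRB. Observed urines give 0, which is the truth only if missed urines are also 40% positive. Letting m vary by arm, the difference is (6 + 10 m_SLB - 8 - 5 m_XRB)/25:

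- m_XRB = 100%, m_SLB = 20%: (6 + 2 - 8 - 5)/25 = -20 points.
- m_XRB = 20%, m_SLB = 100%: (6 + 10 - 8 - 1)/25 = +28 points.

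**The case against.** The strongest reply concerns weight. The outcome is secondary, section 6.4.1 calls the study exploratory, and section 6.4.2 says the sample size will not give a definitive test of efficacy. The gaps of 10 to 20 points are assumed, and the resulting bias is small beside sampling error. Shared compensation, tracking and the expectation that most participants attend Bellevue make a large gap less certain. All of this stands and sets the severity. It does not remove the point: the plan's aim here is an estimate, and sampling error is reported with an estimate, whereas this bias would not be visible.

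A second reply is that missing-as-positive is a defensible rule, since section 6.3.7 recognises a risk of relapse in participants who withdraw. That also stands, and the rule should stay. It supports a high m, but not m = 100% for every missed visit in both arms.

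A third reply is that Timeline Followback measures opioid use too (sections 5.2.2 and 6.2). It uses recall, so a participant who misses one visit and attends the next may still report on the interval. It is therefore of some help, but it is self-report, has no stated look-back window or missing-data rule, and is lost when the participant does not return.

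A fourth is that counts and observed results can be tabulated later from data already collected, and the plan does not forbid it. True; prespecification matters mainly for the range of assumed positivity.

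**Conclusion.** The concern holds as a minor-to-moderate risk of bias in one secondary outcome of a feasibility pilot. Under assumed gaps of 10 to 20 points and equal m of 20% to 80%, the false difference is 2 to 16 points (6 to 12 at m = 40%). It vanishes if missed urines are all positive, or if attendance and m are both equal. The effect on testing is modest; the estimate is the main issue.

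A reader might infer that the rule favours XRB, because injections are given where urine is collected and the planning rates are 71% vs 30%. If those rates were attendance, the false difference at m = 40% would be 0.41 x 0.6 = about 25 points. The documents do not support that reading. The rates are hypothesised retention in community treatment, which can take place outside Bellevue, and are not clinic attendance. Section 6.1.5 says "all participants may elect to continue SLB maintenance with the Bellevue Primary Care Addiction Medicine clinic, or may pursue SLB maintenance from non-NYU/Bellevue" community providers, so XRB participants may leave Bellevue too. Section 6.3.1 says "SLB participants will continue to receive 2-4 week refill prescriptions for SLB from visit 2, week 2 through visit 6, week 8", whereas section 6.3.5 lists the second XRB injection at week 4, depending on the prior injection. That could bring SLB participants to the clinic more often, although the refill sentence is not limited to those treated at Bellevue, so the cue is weak. The direction is open.

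**What to change.** In section 6.4.3, keep missing-as-positive as the main rule for the illicit opioid use outcome. Name that outcome in words, because sections 6.4.1 and 6.4.3 use Aim 2 for retention. Then add:

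1. The number of missing urines by arm and visit.
2. An observed-urine analysis, with a statement that it is also biased if missed urines differ in positivity from attended ones.
3. A sensitivity analysis that varies the positivity of missed urines separately by arm over a prespecified range extending below as well as above the observed positivity, up to 100% (for example 20% to 100%).
4. Timeline Followback reports covering missed visits, where a later visit supplies them, shown descriptively beside the urine result.

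List misses while in custody separately where the custody forms show them; the schedule's notes say those forms may not be filled out. Do not treat custody as proof of no use. Do not recode misses from pharmacy fills: the schedule marks prescription monitoring as SLB only, so recoding could itself bias by arm. The report should say whether the urine conclusion depends on the missing-as-positive rule, without requiring agreement across every scenario.

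The cost is a few sentences and a little more analysis, with no new visits. The downside is wide ranges at N=50, which may show only that the result is uncertain, and a possibly smaller apparent difference between arms.
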